Assessment of binding (non-neutralizing) antibodies (based on immunoassay) as well as neutralizing activity to metreleptin (based on an *in vitro* cell-based assay) has been performed in 2 metreleptin development programs: obesity and lipodystrophy. Prospective assessment of antibody development was specified in the obesity development program and retrospective testing of available samples was conducted in the lipodystrophy program. Anti-metreleptin antibodies have been detected in 70 to 95% of patients who received metreleptin in clinical studies across both programs. Data from the obesity and lipodystrophy programs indicate that, in most patients, anti-metreleptin antibodies occur at a low level (titer), are detected within 4-8 weeks following initiation of treatment, reach a peak titer or plateau within 10 to 20 weeks, and tend to decrease over time despite chronic antigen presentation (due to continued metreleptin therapy), but generally do not disappear completely during therapy. It should be noted that data from the lipodystrophy program generally confirm these findings, but the time course of antibody development and peak titer in lipodystrophy patients is less well-defined due to inconsistent sampling across patients in the clinical studies. In both populations, a small number of patients developed very high anti-metreleptin antibody titers which, in some cases, was associated with *in vitro* metreleptin neutralizing activity.

Confidential Page 16 of 60

To fill some of the void in understanding immunogenicity in patients with generalized lipodystrophy, assessment of the immunogenicity associated with metreleptin treatment in a relevant number of patients was included as a post-approval requirement in the US. The requirement included the following: 1) assessment of anti-metreleptin and anti-human leptin (anti-HuL) binding antibodies when responses peak, 2) assessment of neutralizing antibodies in samples that are confirmed positive for binding antibodies to leptin, and 3) testing for *in vitro* neutralizing activity in patients with loss of effect (worsening metabolic control) or loss of endogenous leptin action (severe infections or sepsis), as well as an analysis of clinical events, over time, associated with binding antibodies or neutralizing antibodies. This study is designed to provide data for these assessments.

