2.2 Rationale for Study Design, Doses and Control Groups

This study is being conducted to satisfy a postmarketing requirement to assess the immunogenicity associated with metreleptin treatment. Because immunogenicity can only be evaluated in the context of drug treatment, the study is open-label and will characterize antibody and *in vitro* neutralizing activity over time and will compare safety and tolerability in patients with different antibody statuses (e.g., binding antibody titer, *in vitro* neutralizing activity category, in vitro neutralizing activity percent inhibition). Immunogenicity will be evaluated in the context of the prescribing information for MYALEPT; thus, the patient population and dosing will be per the US prescribing information (MYALEPT Prescribing Information).

Anti-metreleptin and anti-HuL binding antibody titers over time will be evaluated in order to establish a time course of antibody development and to assess the development of antibodies that recognize the endogenous protein. Because samples from a few patients treated with metreleptin have demonstrated *in vitro* neutralizing activity in an *in vitro* cell-based assay, *in vitro* neutralizing activity will also be assessed in all antibody positive samples. To provide an orthogonal method to evaluate potential *in vitro* neutralizing activity, all antibody positive samples will also be assessed using a ligand-binding assay.

Safety and tolerability of metreleptin associated with the development of, or absence of, antibodies will be evaluated. All adverse events (AEs) will be collected throughout the course of this study. Serious adverse events (SAEs), adverse events of special interest

Confidential Page 17 of 60

(AESI) AEs leading to discontinuation, standard laboratory tests and vital signs will be collected over time and analyzed for any potential association with antibody status. See Section 8.2 for definitions of AEs and AESIs

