#### 17.1 Adverse Events

Adverse Events (AEs) will be coded using the latest version of MedDRA, and summarized by SOC, preferred name, and intensity. Intensity is captured in the CRF. See **Section 8.1** Statistical Tests and Confidence Intervals for a description of summaries to be reported.

Adverse Events of Special Interest (AESIs) are defined as:

- The presence of Category D or E *in vitro* cell-based NAb activity (or the relevant corresponding test result from the ligand-binding method) to metreleptin
- Necrotizing pancreatitis
- Hepatic adverse events including potential drug induced liver injury (DILI)
- Severe hypoglycemia
- Severe hypersensitivity reactions
- New diagnoses of autoimmune disorders (for instance, autoimmune hepatitis, glomerulonephritis, lupus erythematosus, antiphospholipid antibody syndrome, rheumatoid arthritis)
- Autoimmune disease exacerbation
- Serious infection resulting in hospitalization
- All cancers (excluding non-melanoma skin cancer) by cancer type
- Exposed pregnancies and pregnancy outcomes.

TEAEs are defined as AEs that started or worsened in severity on or after the first dose of study medication. If it is unclear whether or not an AE is a TEAE due to partial dates, the worst case will be assumed (i.e., TEAE). See **Appendix 1** for handling of partial dates.

AEs, serious AEs (SAEs), AEs of special interest (AESIs), TEAEs, AEs possibly caused by metreleptin, and AEs leading to metreleptin discontinuation will be summarized by ADA positivity and titer, cell-based NAb positivity and titer, and RB positivity, titer, and quintile of percent

Document: Statistical Analysis Plan: AEGR-734-401: A 36-Month, Multicenter, Open Label Phase 4 Study to Evaluate the

Immunogenicity of Daily SC Metreleptin Treatment in Patients with Generalized Lipodystrophy

Author: [name], [name], [name], [name] Version Number: 2.1

inhibition. For each patient, only one event of each type will be selected to include in summary outputs. If a patient has multiple events the same type, the event with the highest severity level is selected. For patients with multiple events of the same type and severity, the event corresponding to the highest titer or percent inhibition level is selected. The corresponding titer and percent inhibition level are defined by the most recent measurement occurring prior to the event start date.

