### Changes documented in 16Dec2024 version (prior to DBL)

1. Update definition of EAS from:

[E]nrolled subjects who received at least one documented dose of metreleptin and who have baseline and post-dose laboratory results on the measure of interest at the time point of interest.

To:

Enrolled subjects who received at least one documented dose of metreleptin and who have at least one anti-metreleptin/anti-HuL binding antibody (Antidrug Antibody (ADA) binding) result.

2. Update the following analysis from:

AEs, serious AEs (SAEs), AEs of special interest (AESIs), TEAEs, AEs possibly caused by metreleptin, and AEs leading to metreleptin discontinuation will be summarized by ADA positivity and titer, cell-based NAb positivity and titer, and RB positivity, titer, and quintile of percent inhibition.

To:

TEAEs, serious TEAEs, TEAEs that are AEs of special interest (AESIs), TEAEs possibly caused by metreleptin, and TEAEs leading to metreleptin discontinuation will be summarized by ADA positivity and titer, cell-based NAb positivity and titer, and RB positivity, titer, and quintile of percent inhibition.

3. Update analysis windows such that data collected for a CRF-defined visit are windowed according to the CRF-defined visit. Previously analysis windows ended on the same day as CRF-defined visit windows and extended CRF-defined windows to cover the calendar space since the last CRF-defined visit. Analysis windows are updated to extend CRF-defined visit windows to cover calendar space on either side of the CRF-defined visit window. See updated windows in Table 1 below.

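### Adverse events are tabulated by a changing antibody state with no time at risk per state, so most would fall under ADA positive even with no antibody effect

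*SAP*

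**What the plan says.** SAP section 17.1 ends its list of event classes by stating that "AEs leading to metreleptin discontinuation will be summarized by ADA positivity and titer, cell-based NAb positivity and titer, and RB positivity". It assigns the antibody state for these adverse-event tables as follows: "The corresponding titer and percent inhibition level are defined by the most recent measurement occurring prior to the event start date". It then thins the events: "For each patient, only one event of each type will be selected to include in summary outputs". The most severe event is kept, and among events of equal severity "the event corresponding to the highest titer or percent inhibition level is selected". Item 2 of the change form (version of 16 December 2024) limits the tables to treatment-emergent events but keeps the structure: "TEAEs leading to metreleptin discontinuation will be summarized by ADA positivity and titer, cell-based NAb positivity and titer, and RB positivity".

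The statistics are those of SAP section 8.1: counts and percentages for categorical variables. SAP section 14 gives two exposure durations, overall and net of interruptions, neither split by antibody state.

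The protocol sets the purpose. Section 2.1 records the postmarketing requirement, which includes neutralizing-activity testing "as well as an analysis of clinical events, over time, associated with binding antibodies or neutralizing antibodies". Section 2.2 says the study "will compare safety and tolerability in patients with different antibody statuses". Section 2.1 also says that in most patients antibodies "are detected within 4-8 weeks following initiation of treatment" and generally persist while therapy continues.

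Protocol section 10.5 planned something different for serious events, AESIs and events leading to discontinuation: summaries by peak titer, which is fixed for each patient. SAP section 4.3 nonetheless reports no changes from the protocol.

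**The concern.** A patient who seroconverts is ADA negative for roughly the first one or two months and ADA positive for the remaining 34 or 35. Every event before the first positive sample goes to the negative row and every later event to the positive row. Without time at risk, the table shows how long patients spent in each state, mixed with how long they had been on drug. It does not isolate an association with antibodies.

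This can mislead in either direction. A surplus of events in the positive row can look like antibody-related harm when it reflects only duration. Conversely, if some event types cluster early in treatment, they are filed as negative and can mask a real excess later. The percentages have no stated denominator either, since one patient spends time in several states and can appear in different rows for different event types.

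These tables are how the SAP addresses the first safety objective, so a reader will look to them for the answer.

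**Working it through.** Section 17.1 states no figure to reproduce. The check asks what the tables would show if antibodies had no effect and events occurred at a constant rate.

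**Inputs**
- Share of patients ever ADA positive, p: 0.70 to 0.95 (Protocol 2.1). Table 5 in Protocol 10.2 expects 1 of 10 patients at maximum titer 0, so p = 0.90.
- Month of first positive sample, m: detection at 4 to 8 weeks falls at the planned Month 1 or Month 2 visit.
- Follow-up: 36 months.
- Assumption: positivity persists to Month 36.

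**Expected share of post-dose events filed as ADA positive** = p × (36 − m)/36. The event rate cancels.

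| p | m = 1 | m = 2 |
|---|---|---|
| 0.70 | 0.70 × 35/36 = 68% | 0.70 × 34/36 = 66% |
| 0.90 (Table 5) | 0.90 × 35/36 = 88% | 0.90 × 34/36 = 85% |
| 0.95 | 0.95 × 35/36 = 92% | 0.95 × 34/36 = 90% |

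Among seroconverters alone the share is 34/36 = 94% to 35/36 = 97%. If the first positive sample came only at Month 4, the factor is 32/36 and the shares are 62%, 80% and 84%.

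**Would a patient denominator be enough?** No. Take a seroconverter first positive at Month 2, with an assumed rate of 1 event per patient-year (not in the documents). The chance of at least one event is 1 − exp(−2/12) = 15% while negative and 1 − exp(−34/12) = 94% while positive. At 0.5 per year these are 8% and 76%; at 2 per year, 28% and 99.7%. Patient-time is needed.

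**Effect of patient-time.** With 10 patients, 30 patient-years, p = 0.90, m = 2 and 1 event per patient-year, the positive state holds 0.85 × 30 = 25.5 patient-years and 25.5 expected events; the negative state holds 4.5 and 4.5. The raw split is 85% to 15%; the rate ratio is 1.0. Over the range of p and m, the positive state holds 19.8 to 27.7 of the 30 patient-years.

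**Effect of the selection rules.** A simulation applied the severity and highest-titer rules at assumed rates of 0.5, 1 and 3 events per patient-year, with an assumed severity mix and rise-and-wane titer profile. The ADA-positive share became 67–69% (p = 0.70, m = 2), 86–88% (p = 0.90, m = 2) and 93–94% (p = 0.95, m = 1), a rise of about 0.5 to 3 points. At p = 0.90 and 1 event per patient-year, the top titer step held about 19% of selected events against 13% of all events.

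**Category D or E.** Protocol 2.2 gives first detection at 20 to 156 weeks. Within a patient who reaches it, the share of follow-up spent there is (156 − onset week)/156, from 136/156 = 87% down to 0%. The protocol calls such activity infrequent. If, as an illustration, 1 patient in 10 reached it at week 20, the state would hold 0.1 × 136/156 = 8.7% of all patient-time. Most events would then fall outside D/E, again through time alone.

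**The case against.** The study is small and descriptive. No hypothesis is tested and no decision depends on these tables. Protocol 10.5 also plans per-patient plots of titer, neutralizing activity and exposure over time, and summaries by peak titer; the SAP does not expressly withdraw them. With about 11 patients, a careful reader can follow individuals. That stands, and it limits the harm to misreading. It does not repair the tables, because plots supply no denominator and section 17.1 tabulates by a different grouping from the protocol's.

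The table shells (SAP section 9) and parts of the change form are not in the text available and might define denominators. That limits certainty but does not rebut what sections 8.1, 14 and 17.1 say.

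The inputs are soft. The 70 to 95% comes from earlier programs, the protocol says timing in lipodystrophy is less well defined, and persistence is described only during therapy while patients may stop drug and stay in the study. This is why a range is given, with the Month 4 case.

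A reader might infer that almost all events will be filed as antibody positive. The documents support that only among seroconverters (94 to 97%) or near the top of the ever-positive range; across all patients the figure is about two thirds to 92%. Nor does the ADA direction carry over to high-positive NAb, where it reverses.

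**Conclusion.** The concern holds in a limited form. On the visible text, the tables confound antibody state with time spent in it. With no antibody effect, most post-dose events, roughly 66 to 92% and 85 to 88% on Table 5, would sit under ADA positive; for Category D or E most would sit outside the state. The size rests on a constant event rate, first detection at Month 1 or 2, and persistence to Month 36.

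It would go too far to say that the tables will produce a spurious safety finding. Nothing is tested, and the SAP attaches no conclusion to the counts. The defect is that the tables cannot answer the question they are set, and a reader could take duration for association.

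**What to change.** In SAP section 17.1, keep the counts and add for each antibody state:
- the number of patients ever in it;
- the patient-time in it, carried from each sample to the next, with ADA-negative time counted as NAb and RB negative (Protocol 7.3.1 and SAP 15.1 test those only in ADA-positive samples);
- events per patient-year, using either all events or first events with time censored at the event, in place of the one-event and highest-titer selection. Any interval is safer on first events, since a Poisson interval on all events treats repeats in one patient as independent.

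Exclude the Category D or E laboratory result from AESI rates by NAb state, because it is itself an AESI and the comparison would be circular. Show the protocol's peak-titer summary alongside.

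Do not rely on a version restricted to follow-up after Month 2. On Table 5 it would leave about one negative patient and 34/12 = 2.8 negative patient-years. Drop it or give a listing.

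The change form records changes after database lock, so present this as a labelled supplementary table. Note that rates from about 11 patients are imprecise, that the state between visits is assumed constant, and that early-treatment time dominates ADA-negative time in seroconverters. The cost is SAP wording and modest programming from sample, event and follow-up dates already collected.

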8.2 Definitions of Serious Adverse Events

An SAE is an AE occurring during any study phase (i.e., run-in, treatment, wash-out, follow-up), that fulfills one or more of the following criteria:

- Results in death
- Is immediately life-threatening
- Requires in-patient hospitalization or prolongation of existing hospitalization
- Results in persistent or significant disability/incapacity or substantial disruption of the ability to conduct normal life functions
- Is a congenital abnormality or birth defect
- Is an important medical event that may jeopardize the patient or may require medical intervention to prevent one of the outcomes listed above

For further guidance on the definition of an SAE, refer to Appendix A.

In addition, for the purposes of this protocol, the following adverse events of special interest (AESI) must be handled as SAEs and are reportable to Aegerion or designee (see Section 8.6) within the SAE timeframe regardless whether the adverse events did not meet the serious criteria described above in this section:

- The presence of Category D or E *in vitro* neutralizing activity (or the relevant corresponding test result from the ligand-binding method) to metreleptin
- Necrotizing pancreatitis
- Hepatic adverse events including potential DILI

Confidential Page 37 of 58

- Severe hypoglycaemia
- Severe hypersensitivity reactions
- New diagnoses of autoimmune disorders (for instance, autoimmune hepatitis, glomerulonephritis, lupus erythematosus, antiphospholipid antibody syndrome, rheumatoid arthritis)
- Autoimmune disease exacerbation
- Serious infection resulting in hospitalization
- All cancers (excluding non-melanoma skin cancer) by cancer type
- Exposed pregnancies and pregnancy outcomes

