10.5 Methods for Statistical Analyses

There will be no hypothesis testing. All data will be summarized by descriptive statistics and/or listings. In general, continuous variables will be summarized by n, mean, SD, median, min and max. Number of patients and percentage of patients in a category will be provided.

Descriptive statistics will be provided for immunogenicity variables (Section 10.4). The maximum antibody titer (anti-metreleptin or anti-HuL) during a visit will be summarized by visit. Categorization of *in vitro* neutralizing activity as assessed by cell-based assay will be summarized across visits; the rate of Category D and E *in vitro* neutralizing activity with 90% and 80% exact confidence intervals will be computed. The results are reported as percent inhibition and 80% inhibition is currently utilized as the neutralizing antibody threshold. activity Results for *in vitro* neutralizing activity will be summarized across visits; however, there will be no formal comparison of the 2 assay methods for the detection and relative potency of Category D or E *in vitro* neutralizing activity.

Maximum antibody titers, neutralizing activities detected by both methods, and metreleptin exposure for each patient will be plotted over time. Maximum antibody

Confidential Page 47 of 58

titers, neutralizing activities detected by both methods, and any associated clinical events (i.e., loss of efficacy or AE) will be summarized.

All AEs will be coded using the Medical Dictionary for Regulatory Activities (MedDRA). The number and percentage of patients who experienced at least 1 AE will be summarized by system organ class and preferred term. AEs will be summarized by relationship to the study medication and by severity. Deaths, SAEs, AESIs, and AEs leading to discontinuation will be tabulated and/or listed. SAEs, AESIs and AEs leading to discontinuation will be summarized respectively by peak antibody titers (antimetreleptin, anti-HuL) and by *in vitro* neutralizing activity categories or percent inhibition.

Clinical laboratory results (hematology, chemistry, and urinalysis), and vital signs results will be summarized using descriptive statistics for each visit.

Change from baseline in HbA1c and percent change from baseline in fasting triglycerides will be summarized for each visit by overall patient population, by peak antibody titers (anti-metreleptin, anti HuL), and by *in vitro* neutralizing activity categories or percent inhibition , respectively.

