### 4.3 Changes to Analysis from Protocol

There are no changes to the analysis from the protocol.

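### SAP 17.1 groups adverse events by the last antibody result before onset and breaks ties by highest titer, where protocol 10.5 uses peak titer; SAP 4.3 declares no change (minor)

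*SAP*

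**What the plan says.** Protocol 10.5 plans that "SAEs, AESIs and AEs leading to discontinuation will be summarized respectively by peak antibody titers", for anti-metreleptin and anti-HuL, and also by "neutralizing activity categories or percent inhibition". The same section links maximum titers to clinical events: "neutralizing activities detected by both methods, and any associated clinical events (i.e., loss of efficacy or AE) will be summarized".

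SAP 17.1 lays out a different route. One event of each type is kept per patient. The first criterion is severity: "If a patient has multiple events the same type, the event with the highest severity level is selected". The second is the antibody level: "For patients with multiple events of the same type and severity, the event corresponding to the highest titer or percent inhibition level is selected". The level attached to an event is then fixed by timing: "The corresponding titer and percent inhibition level are defined by the most recent measurement occurring prior to the event start date". Peak titer is not mentioned in 17.1, although SAP 15.2 derives peak ADA, NAb and RB.

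On departures from the protocol, SAP 4.3 states: "There are no changes to the analysis from the protocol". SAP 2 gives the SAP precedence where methods differ. The modification history records the event-selection logic as new in version 2.0 of the SAP, but not as a departure from the protocol. In the part of the change form that can be read, the December 2024 item on these tables limits them to treatment-emergent events and leaves the selection and timing rules alone.

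**The concern.** These are the tables that serve the first safety objective, which relates safety to antibody status. Two features affect how they read.

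First, the grouping variable has changed. A patient's peak titer is one fixed value for the whole study. The last result before onset varies from event to event. The same event can therefore sit in different rows under the two rules, and a reader who relies on SAP 4.3 would take the tables for the protocol's analysis.

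Second, the tie-break uses the stratifying variable to decide which event is counted. Where a patient has tied events at different titers, the higher stratum always receives the count. With about 11 patients and up to seven ADA levels, a reader cannot separate the filing rule from a pattern in the data.

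A smaller matter is that one AESI is itself an assay finding, listed in protocol 8.2 as "The presence of Category D or E" neutralizing activity. In tables stratified by NAb or RB result, the event and the stratum come from the same assays, and neither document defines the onset date of this event.

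**Working it through.** There is no plan figure to reproduce, because the point rests on the text. The numbers below only size it.

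**1. Grouping rule, side by side.** The protocol files by patient peak, and the SAP by last result before event start. An invented course on the visit schedule shows the difference: negative at Month 0, then 1:10, 1:50, 1:250 and 1:6250 at Months 1, 2, 4 and 6, falling to 1:250 by Month 18.

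| Event at | SAP 17.1 files under | Peak |
|---|---|---|
| Month 0.5 | negative | 1:6250 |
| Month 3 | 1:50 | 1:6250 |
| Month 5 | 1:250 | 1:6250 |
| Month 8 | 1:6250 | 1:6250 |
| Month 20 | 1:250 | 1:6250 |

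The rules agree only when the last prior result is the peak. The conflict is explicit for binding titers only. For neutralizing categories and percent inhibition, protocol 10.5 names no time point.

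**2. Share of events before the peak.** Inputs are 1 of 10 patients never positive (protocol Table 5) and, as an assumption, events spread evenly over patients and over 36 months (156 weeks). The share is 0.9 × time to peak / study length.
- Protocol 2.1, 10 to 20 weeks: 0.9 × 10/156 = 5.8%; 0.9 × 20/156 = 11.5%.
- Protocol 10.2, 4 to 7 months: 0.9 × 4/36 = 10.0%; 0.9 × 7/36 = 17.5%.

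The range is about 6% to 17.5%. Events after a later fall in titer, which protocol 2.1 describes as usual, would also be filed below the peak.

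**3. Tie-break.** The largest of several values is never below the one a titer-blind rule would pick, so the direction is certain. For two tied events, let q be the chance that an event's titer is at or above a given cut, and r the within-patient correlation of that status. Then P(filed at or above the cut) = q + q(1−q)(1−r), a rise of q(1−q)(1−r).

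Protocol Table 5 gives anchors for q: (3+2+0)/10 = 0.5 at ≥625 and (2+0)/10 = 0.2 at ≥3125. These are whole-study maxima on the protocol's titer scale, so q at event time may be lower. The values of r and of tie frequency are assumed.

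| q | r | Rise among tied patients | Overall, 10% tied | Overall, 50% tied |
|---|---|---|---|---|
| 0.5 | 0.5 | 12.5 points | 1.25 | 6.25 |
| 0.5 | 0.8 | 5.0 | 0.50 | 2.5 |
| 0.2 | 0.5 | 8.0 | 0.80 | 4.0 |
| 0.2 | 0.8 | 3.2 | 0.32 | 1.6 |

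If all 11 patients in SAP 4.1 had the event type, the largest entry is 0.0625 × 11 = 0.69 patient and the smallest is 0.0032 × 11 = 0.04. One whole patient is reached only under harsher assumptions. With three tied events (beta-binomial, q = 0.5, r = 0.5) the rise is 18.75 points, and half of the patients tied gives 0.1875 × 0.5 × 11 = 1.03. With two independent titers (r = 0, q = 0.5) it is 0.25 × 0.5 × 11 = 1.4, but serial titers in one patient are unlikely to be independent.

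**The case against.** The case on the other side is substantial.

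- Filing by the last prior result is sound on temporal grounds, because a whole-study peak may come after the event it is meant to explain. SAP 2 lets the SAP govern. Both points stand, so the timing rule itself is not called wrong.
- The tie-break is stated openly, resembles the SAP's other worst-case conventions, and can never file an event above the patient's own peak. This also stands. It makes the rule transparent, but the rule still selects on the stratifying variable.
- The size is small and its inputs are assumed, and the study tests no hypotheses. This stands and sets the severity.
- The Category D/E overlap comes from protocol 8.2 and 10.5, and an AE start date is collected for AESIs. This stands, so what is left is a missing onset definition.
- The table shells and parts of the change form were not available, and they may hold a peak-titer table or a correction. This cannot be ruled out.

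None of this makes SAP 4.3 accurate. A precedence clause decides which rule applies when documents differ; it does not remove the difference.

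**Conclusion.** The point holds as a minor one. For binding titers, SAP 17.1 departs from protocol 10.5 while SAP 4.3 reports no change. The tie-break selects on the variable used for stratification, so its direction is certain. Its size is probably below one patient of 11, given the assumed correlations and ties in no more than half of patients. The 6% to 17.5% of events before the peak rests on evenly spread events and the Table 5 expectation.

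A reader might infer that the safety tables are biased toward an association with antibodies. The documents do not support that: last-prior filing lowers some events relative to peak while the tie-break raises others relative to a titer-blind choice, and no net direction follows. A reader might also infer that the peak-titer analysis was dropped or that the change was not allowed. The first cannot be shown without the shells, and SAP 2 contradicts the second.

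**What to change.** 1. Replace the highest-titer tie-break with a titer-blind rule, such as earliest onset, and list every event with its titers.
2. Present the protocol's peak-titer tables beside the event-time tables. If the shells already contain them, describe them in SAP 17.1.
3. Amend SAP 4.3 or the change form to declare the departure from protocol 10.5.
4. In the NAb- and RB-stratified tables, footnote that the Category D/E AESI and the stratum share an assay, and state the onset date used. Keep the event in these tables, since the protocol requires them.

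The cost is wording, some programming, one further set of tables and one listing, all from data already collected. The change form dated 26 February 2025 records changes after database lock, so anything added now needs a post-lock label.
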